We anticipate accruing a total of 40 participants locally to achieve a total of 50 participants from both recruitment sites. To obtain a final sample size of $n = 40$, we will enroll $n = 70-90$ to account for dropout or non-completion. We expect to screen approximately 144 individuals to achieve a total accrual of 40 participants.

13. Recruitment Methods

After obtaining approvals, active and passive recruitment for this study will take place at the Georgia Comprehensive Sickle Cell Center at Grady Memorial Hospital (Grady) in Atlanta, Georgia and the James R. Clark Sickle Cell Memorial Foundation (SC Memorial Foundation) in Columbia, South Carolina. Active recruitment by the project coordinator will involve the weekly screening for eligibility and enrollment of adults who receive care in the sickle cell clinic at Grady and who are served by the SC Memorial Foundation. Potential participants will be identified and screened for eligibility, using the inclusion and exclusion criteria, by conducting an initial review of medical records or obtaining patient report. Active recruitment may also occur through healthcare providers and community health workers who inform potential participants about the study, either in person or via mailed opt-in/opt-out letters, if necessary (see attached document), and provide them with contact information for the project coordinator or principal investigator (PI). Passive recruitment will occur via the use of flyers placed at the sickle cell clinic and SC Memorial Foundation to inform potential participants about the study. If necessary, these flyers may also be published on social

Protocol Title: Home-Based Intervention for Chronic Pain in Adults with Sickle Cell Disease (HIPAS)

media including Instagram, Facebook, and Twitter or via a website developed specifically for the study. Interested individuals will be invited to contact the program coordinator or PI, using the contact information provided on the flyers (see attached document), for further information. In the event of any enrollment shortfalls, we will do the following to achieve recruitment goals: consider loosening the exclusion criteria, expand the study to an additional sickle cell clinic, utilize area resources to increase the efficiency of participant enrollment, and/or extend the recruitment period.

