Electronic methods, including REDCap and Microsoft Office, will be used to organize and manage data collected from this study. A data collection log will be used to enable tracking of data collection activities. Data collection logs will specify what data are to be collected for each participant, using which instruments, with expected and actual dates of data collection. Detailed reports of completed instruments listed by participant identification number will be generated for program management purposes; for instance, to plan for conducting focus group sessions or individual interviews.

Data Analysis

Data will be collected and managed by using REDCap. All quantitative data will be verified and periodic quality assurance checks of data entry will be performed. Once finalized, data will be exported from REDCap into the Statistical Package for the Social Sciences (SPSS Version 26) for statistical analysis. We will code the surveys manually and evaluate their psychometric properties in the sample. Initial data analysis will include descriptive statistics (e.g., means, standard deviations, frequencies, and percentages) on sample characteristics and outcomes at each time point. To ensure balance in participants' characteristics by intervention group at baseline, we will compare the sociodemographic and clinical characteristics (e.g., age, gender, disease severity, and comorbidities) of participants using t-tests or chi-square tests as appropriate. Any differences across treatment groups will be accounted for in subsequent analysis. We will also evaluate any attrition according to participants' characteristics. We will assess distributional assumptions of outcomes and perform appropriate transformations to remedy any violations. We will minimize missing data by monitoring data regularly and implementing successful methods for obtaining follow-up data. When data cannot be collected, sensitivity analysis will be performed to evaluate the impact of missing data on results. We also plan to use the restricted maximum likelihood (REML) method for model estimation whenever possible to minimize the impact of missing data. All outcomes will be compared among participants in both arms. All statistical tests will be two-sided and intent-to-treat procedures

Protocol Title: Home-Based Intervention for Chronic Pain in Adults with Sickle Cell Disease (HIPAS)

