will be employed. Additionally, all analyses will include sex (male vs female) as a biological variable to assess differences in outcomes within each group.

Number and percent will be used to summarize the primary feasibility measures while content analysis will be used to summarize the secondary feasibility measures. Optimal treatment will be determined by correlations among the engagement outcomes and measures of preliminary efficacy. We will use mixed-effects models to test whether the outcomes differ across the treatment group over time (from pre- to post intervention). Depending on the type of outcome (continuous or categorical), linear or generalized mixed effects models will be used, respectively. In this approach, each participant is treated as an experimental unit with repeated observations over time. The model will include fixed effects of time, intervention group, and time x intervention group interaction, and assume an unstructured variance-covariance matrix to describe the covariance structure. We will adjust for any baseline group differences in participant characteristics. A significant interaction effect will indicate significant differences in outcomes by treatment groups over time. We will select the most parsimonious model using Akaike information criterion (AIC) and Bayesian information criterion (BIC). Hypotheses tests based on specific contrasts in the mixed model and the interaction term between time and intervention group will be performed to test whether subjects in the intervention group demonstrated improved outcomes compared to the control group. The model-based estimates of the outcome measures for the two treatment groups at each time point will be used to estimate effect sizes for future studies.

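### The efficacy model does not pre-specify adjustment for the baseline outcome score, so it gives up some precision; the plan stays valid, and the size of the loss depends on a correlation and SDs that the documents do not give.

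*Combined protocol and SAP*

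**What the plan says.** The combined protocol and SAP, section 18 (Data Analysis), sets out mixed-effects models to "test whether the outcomes differ across the treatment group over time (from pre- to post intervention"). The specification is: "The model will include fixed effects of time, intervention group, and time x intervention group interaction, and assume an unstructured variance-covariance matrix".

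Two uses of the model follow. For testing: "Hypotheses tests based on specific contrasts in the mixed model and the interaction term between time and intervention group will be performed". For planning the next trial: "The model-based estimates of the outcome measures for the two treatment groups at each time point will be used to estimate effect sizes". The levels of time and the contrasts are not listed.

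Section 18 also plans some adjustment. The arms are compared at baseline on sociodemographic and clinical characteristics, with age, gender, disease severity and comorbidities as examples, and characteristics that differ are then adjusted for. Sex is included in all analyses. No sentence makes the baseline value of the outcome a covariate or constrains the arms to a common baseline mean.

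On estimation and population, the same section says "We also plan to use the restricted maximum likelihood (REML) method for model estimation whenever possible to minimize the impact of missing data" and "All statistical tests will be two-sided and intent-to-treat procedures" will be used. Section 4 names pain catastrophizing as the primary measure of pain coping, which is the primary outcome. Table 1 collects it at baseline and at weeks 4, 8 and 12, and section 6 places the baseline questionnaires before randomisation.

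**The concern.** With baseline as a response and a free group effect, each arm has its own baseline mean. The time by group contrast is then the difference between arms in change from baseline. That contrast subtracts the whole baseline difference between arms, although chance imbalance at baseline predicts only part of the later difference. Adjusting for the baseline score subtracts the part that the data support.

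Precision per completer is costly here. Section 12 says "we will enroll $n = 70-90$ to account for dropout or non-completion" in order to finish with 40, an implied loss of 43% (1 − 40/70) to 56% (1 − 40/90). Estimating effect sizes for later studies is one stated use of the data, although the Study Summary puts feasibility and acceptability alongside preliminary efficacy and Aim 1 is feasibility. The covariate is already collected, so any precision it brings is nearly free.

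**Working it through.** **Inputs from the documents.** 40 completers randomised 1:1, taken as n = 20 per arm; 70–90 enrolled, midpoint 80, so N = 40 per arm; d = 0.9, 80% power, 5% level (Revision History, entry dated 10/28/2022); two-sided tests (section 18).

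**Assumed, because the documents are silent.** Baseline to week 8 correlation r = 0.3, 0.5 or 0.7; SD 1 at both times; dropout at random, with dropouts giving baseline only.

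**The plan's own figure.** For an arm difference at one visit that ignores baseline, SE = √(2/20) = 0.316. The detectable difference is (1.960 + 0.842) × 0.316 = 0.886, or 0.909 with the noncentral t. Power at 0.9 is 81.2% (normal) or 79.2% (t). The stated d = 0.9 reproduces.

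**Variances.** Let A = 2(1 − r²)/n and S = (1 − r²) × 2(1/n − 1/N)/36, where S is the cost of estimating the slope.
- Difference in change: A + S + 2(1 − r)²/N
- Arm difference at week 8 from the planned model: A + S + 2r²/N
- Baseline-adjusted difference: A × (1 + 1/36)

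At r = 0.5: A = 2 × 0.75/20 = 0.0750 and S = 0.75 × 2 × 0.025/36 = 0.0010. Change = 0.0750 + 0.0010 + 2 × 0.25/40 = 0.0885. Adjusted = 0.0750 × 37/36 = 0.0771. The ratio is 0.871.

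| | r = 0.3 | r = 0.5 | r = 0.7 |
|---|---|---|---|
| SE, change | 0.342 | 0.298 | 0.237 |
| SE, arm difference at the visit | 0.311 | 0.298 | 0.276 |
| SE, adjusted | 0.306 | 0.278 | 0.229 |
| Variance ratio, adjusted/change | 0.801 | 0.871 | 0.933 |
| Variance ratio, adjusted/visit | 0.967 | 0.871 | 0.688 |
| Power at 0.9, change (t, 37 df) | 73% | 84% | 96% |
| Power at 0.9, adjusted (t, 37 df) | 82% | 88% | 97% |

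Simulation (40,000 trials per cell) gave SEs of 0.341/0.299/0.238 for change and 0.305/0.279/0.230 for adjusted. Across 70–90 enrolled, the ratio to change is 0.779–0.819, 0.855–0.883 and 0.924–0.940. Against the change contrast the gain equals about 10, 6 and 3 completers (40/0.801 = 49.9; 40/0.871 = 45.9; 40/0.933 = 42.9).

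**Unequal SDs.** Let the week 8 SD be k times the baseline SD. Change becomes k²(A + S) + 2(1 − rk)²/N and adjusted becomes k²A × 37/36. At k = 1.2 and r = 0.7: change = 1.44 × 0.05171 + 2 × 0.16²/40 = 0.0757; adjusted = 1.44 × 0.05242 = 0.0755; ratio 0.997.
- k = 1.2: ratio to change 0.878/0.945/0.997 at r = 0.3/0.5/0.7, and 1.01 at r = 0.8.
- k = 0.8: ratio to change 0.68/0.74/0.78.
- The ratio to the arm difference at the visit does not depend on k, since every term scales by k².

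**Standardising SD.** Dividing the adjusted difference by the residual SD instead of the outcome SD multiplies d by 1/√(1 − r²) = 1.05, 1.15 and 1.40.

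**The case against.** The planned model is a standard longitudinal model and the trial is a pilot whose first aim is feasibility, so preferring baseline adjustment is partly a matter of taste. That stands, and it caps the weight of the point.

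The plan already promises adjustment, and its list of characteristics is given only as examples, so the baseline score might be meant. Even so, that adjustment would apply only if a difference were observed. Conditional adjustment is not a pre-specified covariate, and none of the examples is the outcome score.

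The effect size for future studies need not be an unadjusted arm difference at each visit. Arm estimates at every time point could equally be combined into a difference in change. This stands: the ratios 0.97/0.87/0.69 hold only on the first reading.

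Three stronger conclusions are tempting and the documents do not support them.
- A reader might infer bias or a wrong error rate. Under randomisation both planned quantities are unbiased, and nothing here shows type I inflation.
- A reader might infer that the sample size is wrong. The stated d = 0.9 for 40 participants reproduces.
- A reader might infer that adjustment always wins. With equal SDs it loses slightly to the change contrast above r of about 0.95, and to the arm difference at the visit below about 0.16. With a larger week 8 SD, the gain over change disappears by r = 0.7.

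**Conclusion.** The point holds as a modest loss of precision. Adjustment for the baseline outcome score is not pre-specified, and under equal SDs and random dropout the adjusted contrast has 7% to 20% less variance than the change contrast over correlations 0.7 to 0.3. Below a correlation of about 0.5 this matters most for the change test. If the effect size is read as an arm difference at each visit, the loss there grows with the correlation, up to 31% of variance at 0.7.

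The direction is not guaranteed, because it rests on a correlation and an SD ratio that the documents do not report. A week 8 SD 0.8 times baseline makes the gain over change larger, and 1.2 times makes it smaller or nil. The plan is usable as written; this is an inexpensive improvement, not a correction of an error.

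**What to change.** For each continuous scale measured at baseline and weeks 4, 8 and 12, pre-specify one REML model for the post-baseline visits. Its fixed effects are visit, group, visit by group, the baseline score of that outcome and its interaction with visit, with the planned sex term kept and an unstructured covariance. Name the visit for the main contrast; week 8 is labelled post-treatment, but no visit is declared primary. Take both the test and the effect size, with a 95% CI, from that baseline-adjusted contrast. Standardise by the pooled baseline SD, not the residual SD.

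**Cost.** One paragraph is reworded and no data are added. The baseline terms use about three parameters, one per visit. Participants with no post-baseline score leave the model, and with the implied losses they may be many. Given the intent-to-treat statement, report their number by arm and cover them in the missing-data sensitivity analysis that section 18 already plans.

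A model with a common baseline mean would keep those participants, but baseline-only records add no precision to the week 8 contrast there either. It also assumes that both arms come from one randomised population. Sections 6 and 15 apply VR eligibility to the VR arm only, while section 10 excludes susceptibility to cybersickness from the whole trial. Until those sections are reconciled with randomisation, the covariate form is preferable; it does not itself repair that inconsistency.
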